**Version 4.2**

## Implementation of EU risk minimisation measures for medicinal products in clinical guidelines

Title	Implementation of EU risk minimisation measures for medicinal products in clinical guidelines
Study ID	EMA/2020/46/TDA/L4.02 (Lot 4: Qualitative research) Specific Contract 01 EUPAS47588
Framework contractor	EU PE&PV research network
Countries of study	Denmark, Greece, Latvia, Netherlands, Portugal, Slovenia
Objectives	
The objectives of this project are to:
 
Identify and describe the key stakeholders, processes, roles and responsibilities for updating clinical guidelines on pharmacological treatment in six European countries
 
Describe and analyse how medicinal product specific RMM for the five disease priority areas and active substances have been integrated in relevant clinical guidelines in six European countries, identifying the key elements of risk minimisation included in new or updated clinical guidelines, key milestones and enablers and barriers for updating, publication/dissemination and adoption of guidelines in healthcare practice
 
Provide recommendations for regulators to engage with healthcare professional bodies and other responsible parties to strengthen the role of clinical guidelines for RMM implementation, outlining feasible concrete steps EMA and national competent authorities could consider.

Scientific contact person	[name], Utrecht University, [contact]
Administrative contact person	[name] [name], Utrecht University, [contact]

## Document version

NAME	DATE	VERSION	DESCRIPTION
Consortium	June 2022	1.0	Study protocol
[name]	July 2022	2.0	Study protocol, version for consortium review
Consortium	July & August 2022	2.0	Review
UU, UCPH	15 August 2022	3.0	Final version for consortium review
Consortium	15-29 August 2022	3.0	Review
UU, UCPH	31 August 2022	4.0	Final version for submission
Consortium	9 October 2022	4.1	Revised implementing EMA comments
Consortium	2 November 2022	4.2	Revised implementing EMA comments

## 1. Title of the study

Implementation of EU risk minimisation measures for medicinal products in clinical guidelines

## 2. List of abbreviations

C	Study coordinator
CP	Contributing partners
CT	Coordinating team
DHPC	Direct Healthcare Professional Communication
DK	Denmark
DMP	Data Management Plan
DPD	Dihydropyrimidine dehydrogenase
DUTH	Democritus University of Thrace
EMA	European Medicines Agency
ENCePP	European Network of Centers for Pharmacoepidemiology and Pharmacovigilance
EU	European Union
GDPR	General Data Protection Regulation
GIN-UGWP	Guidelines International Network's Updating Guidelines Working Group
GR	Greece
LV	Latvia
MS	Member State
NCA	National Competent Authority
NL	The Netherlands
NT	National team
PPP	Pregnancy prevention programme
PT	Portugal
QOREC	COnsolidated criteria for REporting Qualitative research
RFI	Request for information
RMM	Post-marketing risk minimization measure
SC	Steering committee
SI	Slovenia
TA	Therapeutic Area
UCPH	University of Copenhagen
UIPS	Utrecht Institute for Pharmaceutical Sciences
UU	Utrecht University
WP	Work Package

## 4. Abstract

### *Rationale and background*

Post-marketing risk minimization measures (RMMs) upon regulatory request are crucial for providing patients with safe and effective medicines. However, there is significant complexity to implementing RMMs as they seek to modify knowledge and behaviour of a diverse range of individuals and often require articulation with structures and organizations. Clinical guidelines that summarise current medical knowledge and provide evidence-based treatment recommendations for specific therapeutic areas are key documents in the networked governance of medicines safety and RMM implementation. Although ‘best practice’ procedures for updating clinical guidelines include processes for identifying triggering events, which determine thresholds for initiating updates and evidence monitoring practices, the role and extent of RMMs in such processes remain undocumented.

### *Research question and objectives*

This project aims to describe and understand processes for updating clinical guidelines and the role of healthcare professional associations and public bodies involved in the production of clinical guidelines and the dissemination of emergent safety concerns.

Specifically, the objectives of the study are to:

1. *Identify and describe the key stakeholders, processes, roles and responsibilities for updating clinical guidelines on pharmacological treatment in six EU Member States (Denmark, Greece, Latvia, Netherlands, Portugal, Slovenia).*
2. *Describe and analyse how product specific RMMs for five disease priority areas and active substances have been integrated into relevant clinical guidelines in DK, GR, LV, NL, PT and SI.*
3. *Provide recommendations for regulators to engage with healthcare professional bodies and other responsible parties to strengthen the role of clinical guidelines for RMM implementation.*

### *Study design*

A multiple-case study design will be applied, using document content analysis of clinical guidelines combined with qualitative semi-structured interviews with key informants from organizations that produce guidelines as well as representatives from national competent authorities (NCAs).

The methodology involves three components which will be divided over three work packages (WPs): WP1 “Mapping of relevant organisations”, WP2 “Document collection and analysis of clinical guidelines” and WP3 “Key Informant Interviews”. Findings will be analysed by country, therapeutic area, type of population and type of health care provider.

### *Population*

For WP1 and WP2, we will study various types of documents and online materials (text) in each of the six countries. For WP3, we will include representative key informants in the six countries, including stakeholders from national competent authorities, public sector and health authorities, professional associations and expert groups.

### *Variables*

This study will include information about the entities that issue, develop and/or update clinical guidelines identified in WP1 (domains: general information, membership, guideline development), as well as information extracted from clinical guideline documents (document analysis, WP2 – domains: general information, population, target audience, therapeutic area, information on RMM). In addition, semi-structured interviews will be utilized to explore subjective, non-observable dimensions of social relations or work processes to supplement and extend understanding of the results from preceding document analysis (WP3).

### *Data Sources*

Documents and online materials (text) for WP1 and WP2. Transcripts from semi-structured interviews with key informants for WP3.

### *Study Size*

The sample size will depend on the country, but it is estimated that each of the countries will have a range of 7-20 interviewees in total including the various stakeholders.

### *Data analysis*

Content analysis will be conducted using pre-defined coding frameworks (WP1 and WP2). The extent to which information products cover the RMM will be graded based on the results of the coding of information products. Interview transcripts (text) from semi-structured interviews (WP3) will be produced. The analysis of these will involve an inductive content analysis based on a close line-by-line reading of the responses and developing a conceptual coding scheme based on the major themes in an interview guide.

### *Milestones*

Major milestones: “Recruitment of Key informants” (1 January 2023); “Data collection completed” (1 March 2023) and “All results received” (August 2023).

## 5. Amendments and updates

Date	Protocol version	Description

## 6. Milestones

An overview and timeline of project elements, including key milestones and deliverables, in accordance with the accepted Preliminary Study Plan (deliverable D1) is presented in Table 1 and Figure 1. Updates on progress will be communicated during bimonthly meetings between the research team and EMA. In addition, EMA will be informed about the status of milestones in January (recruitment of Key informants & interim results from content analysis), March (data collection completed) and August 2023 (all results received) as these represent critical moments for the project progress.

Table 1: Timeline of key milestones & deliverables

Milestones (M) and Deliverables (D)	Planned date	Actual date
Start of project	NA	19 April 2022
D1: Preliminary study plan	1 July 2022	3 June 2022
M1: Content analysis framework ready to be implemented	1 August 2022	1 August 2022
M2: Interview guide ready	1 September 2022	1 September 2022
D2: Study protocol	1 September 2022	1 September 2022
M3: Local ethical committee applications submitted in all participating countries	1 November 2022	
M4: National overviews of relevant organizations issuing and updating clinical guidelines for the five disease areas	1 November 2022	
M5: Recruitment of key informants completed	1 January 2023	
M6: Data collection completed	1 March 2023	
M7: Coordinating team receives all results from national teams	1 July 2023	
M8: Draft report has been written and agreed upon by consortium	1 August 2023	
D3: Study Report	1 September 2023	
M9: Draft manuscript has been written and agreed upon by consortium	1 October 2023	
D4: Manuscript	6 November 2023	

Timeline	2022							2023										
	May	June	July	Aug	Sept	Oct	Nov	Dec	Jan	Feb	Mar	Apr	May	June	July	Aug	Sept	Oct
Project inception																		
Organization kick-off meeting	C																	
Kick-off meeting	CT																	
Installation Steering Committee	CT																	
Set-up of consortium communication and project meeting schedules	CT																	
Development of preliminary study plan	CT																	
Study plan delivery		D1																
Development of data management plan	CT	CT																
Development of mapping strategy	CT	CT																
Development of content analysis plan	CT	CT	M1															
Development of key informant recruitment plan & materials		CT	CT															
Development of interview guide		CT	CT	M2														
Writing and reviewing of protocol		CT	CT	CT														
Protocol delivery				D2														
Input and review of project plans and materials	CP	CP	CP	CP														
Registration of study and protocol in EU PAS Register				C														
Monitoring progress	CT	CT	CT	CT	CT	CT	CT	CT	CT	CT	CT	CT	CT	CT	CT	CT	CT	CT
Data collection and analysis																		
Mapping of organisations				NT	NT	M3												
Document collection					NT	NT												
Content analysis of guidelines					NT	NT	NT											
Seeking Local Ethical Committee Approval					NT	M4												
Recruitment of key informants						NT	NT	M5										
Interviews in 5 countries						NT	NT	NT	NT	M6								
Extended sampling/ethics assessment delays											NT	NT						
Data analysis interview										NT	NT	NT	NT	NT	M7			
Monitoring process	CT	CT	CT	CT	CT	CT	CT	CT	CT	CT	CT	CT	CT	CT	CT	CT	CT	CT
Reporting																		
Drafting preliminary report												CT	CT	CT	CT			
Review of draft report													CP	CP	M8			
Delivery of final report																D3		
Drafting manuscript													CT	CT	CT	CT	CT	
Manuscript review															CP	CP	M9	
Manuscript delivery																		D4

Figure 1: Overall project timeline. CT: coordination team (UU, UCPH), NT: national teams (UU, UCPH, RSU, UP, UL, DUT), CP; all partners

## 7. Rationale and background

Post-marketing risk minimization measures (RMMs) upon regulatory request are crucial for providing patients with safe and effective medicines. However, there is significant complexity to implementing RMMs as they seek to modify knowledge and behaviour of a diverse range of individuals (i.e., patients, consumers, caregivers and healthcare professionals) and often require articulation with structures and organizations (i.e., health authorities, educational and academic research centres, healthcare professional associations and patient organizations).

These stakeholders are involved in healthcare in different roles and may be situated at international, European, national, or subnational levels. Some stakeholders provide clinical guidance for healthcare practitioners on medicines' safety and its content may coincide with that of RMMs. For example, recent research on additional RMMs suggests that medical reference books and clinical guidelines are prescribers' preferred channels for keeping up to date with the safety information about medicines, and that prescribers rarely refer to regulatory documents directly (1, 2). This indicates that rather than relying on regulatory sources for medicines' safety updates, some healthcare professionals rely on recommendations from other organizations that may produce guidance according to different biomedical, legal, economic, bioethical, and sociocultural considerations. As suggested in recent conceptual work on the EU regulatory network engagement with patients and healthcare professionals, the clinical management of medicines safety can be assumed to depend on a 'risk governance network' of multiple, informally connected organizations (3).

Due to the diverse network of organizations involved in providing clinical guidance on medicines safety, a key factor for RMM implementation is the alignment of RMMs implementation processes with the processes of the different organizations and entities and the compatibility of the RMM information with other sources of medicine safety information. In addition, other important factors include how risk information and risk communication are generated and communicated and the time ensued between the announcement of new safety information and the implementation of measures in practice. Indeed, literature on risk governance networks suggests that the ability of the governance network to provide the intended outcomes depends on the network's capacity and processes for aligning activities and assessments in situations marked by complexity, uncertainty and ambiguity (4).

RMMs go through their own decision-making regulatory pathway at the EMA level, which is then adopted/translated/operationalized at national level by the national competent authorities, eventually implemented by healthcare professionals, and ultimately reaching patients. Thus, to improve RMM implementation and the engagement of the EU regulatory network with relevant stakeholders, it is necessary to understand how clinical guideline development fits that pathway by identifying the key organizations that issue medicine safety guidance and by characterizing their different remits, level of jurisdiction, and perceived roles and responsibilities.

Clinical guidelines that summarise current medical knowledge and provide evidence-based treatment recommendations for specific therapeutic areas are key documents in the networked governance of medicines safety and RMM implementation. They may be issued by public bodies, professional associations, and academic research centres alike, and they play an important role assisting clinicians and patients in their healthcare decisions (Figure 2). However, the connection between RMMs and clinical guidelines has been underexamined. Although 'best practice' procedures for updating clinical guidelines include processes for identifying triggering events, which determine thresholds for initiating updates and evidence monitoring practices (5), the role and extent of RMMs in such processes remain undocumented. Moreover, recent literature on the standardization of clinical guidelines updating processes suggests that there is significant variation in how guideline developers operate, nationally and according to their organizational remits (6). Thus, in addition to identifying and describing key guidance organizations, an

important step to improve RMM implementation is to gain better understanding of how RMMs feature and are incorporated in the development of clinical guidelines at the organizational level, and more specifically in their processes for guideline revision.

[figure not shown]

Figure 2. Example of mapping of sources and channels for medicines guidelines for general practitioners in Denmark. Adapted from the National Audit Office (2021).

Whether or not RMMs are adopted into clinical guidelines is also determined by the compatibility and utility of the documents and information provided as part of the RMM (e.g., communication about regulatory actions, product information). The communication channels through which guideline developers receive RMM documents warrant further examination to ascertain whether risk communication measures and materials from regulatory authorities are being consulted and used when updating clinical guidelines.

Several disease areas and their indicated pharmaceutical products have posed important emergent drug safety risks and therefore required further implementation of RMMs. For this specific project, the focus is on:

- Neurological diseases/Valproate (2018) followed by a pregnancy prevention programme (PPP) (7);
- Infectious diseases/(Fluoro-)Quinolones followed by restrictions in use (2019) (8);
- Inflammatory, autoimmune and cancer diseases/Methotrexate with a measure to prevent dosing errors (2019)(9);
- Chronic disease: Diabetes/Metformin (2016) followed by a measure to monitor kidney function of certain patients (10);
- and Cancer diseases/Fluorouracil and related substances guiding to test for lack of dihydropyrimidine dehydrogenase (DPD) before starting fluorouracil, capecitabine, tegafur or flucytosine by injection or infusion (2020) (11).

An overview of the RMMs for these medicinal products can be found in Appendix I. Since these areas have been subject to prominent post-marketing risk communication, and regard various types of diseases and

therefore diverse healthcare prescribers, they are appropriate to study the diffusion of emergent safety information at national level.

This research, therefore, aims to investigate the role played by national health and regulatory authorities, national clinical guideline developers and (inter)national professional associations or expert groups in a selected group of European countries spread across Europe and with differences in healthcare systems when communicating emerging safety information. We will focus on identifying the networks and channels through which these entities receive and disseminate safety information. We will also identify the key factors (enablers and barriers) influencing how individual entities decide whether safety information is sufficiently serious to act on or disseminate to members and/or the wider public. This includes assessment of the key elements of the risk minimization measure that are included in new or updated clinical guidelines. To explore the variety of diffusion strategies for emergent drug safety information, we will focus on a set of five disease areas and medicines which have been subject to post-marketing risk communication measures. These medicines are prescribed and or dispensed by different types of health care providers, including general practitioners, specialists, nurses and pharmacists. These will be further examined in parallel in six European countries, resulting in 30 case studies (five per country) in total.

The overall aim of the study is to describe and understand processes for updating clinical guidelines and the role of healthcare professional associations and public bodies involved in the production of clinical guidelines and the dissemination of emergent safety concerns. From this knowledge we will produce recommendations for regulators to engage with healthcare professional bodies and other responsible parties to strengthen the role to be played by clinical guidelines in RMM implementation, outlining feasible concrete steps that EMA and national competent authorities could consider.

## 8. Research question and objectives

The study aims to describe the key elements of risk minimisation measures included in clinical guidelines, processes for updating clinical guidelines with regulatory action and the role of clinical guidelines in the implementation of product specific RMMs. These findings will be applied to derive recommendations for strengthening the role of EMA and national competent authorities therein.

In this context, the impact of regulatory actions means investigating the role of clinical guidelines as to the implementation of product specific RMM in six EU Member States – Denmark (DK), Greece (GR), Latvia (LV), Netherlands (NL), Portugal (PT) and Slovenia (SI).

Specifically, the objectives of the study are to:

**1. Identify and describe the key stakeholders, processes, roles and responsibilities for issuing clinical guidelines** on pharmacological treatment in DK, GR, LV, NL, PT and SI. Focus will be on:

- a) Key bodies and organisations responsible for issuing clinical guidelines, including national guideline committees and any other responsible bodies at local, national or European level;
- b) Key triggers (e.g., publications, regulatory communications), processes and timelines for updating and publishing clinical guidelines on pharmacological treatment, including communication channels between responsible bodies and organisations and the EU regulatory network institutions;
- c) Key regulatory documents relating to the five disease priority areas and active substances (e.g., public statements on regulatory actions, product information, see Appendix I) and RMM materials used for updating clinical guidelines including their utility;

- d) Key differences between countries and therapeutic areas relating to the five disease priority areas and active substances, including enablers and barriers for updating, publication/dissemination and adoption of guidelines in healthcare practice.

Product specific RMMs (objective 2) will be used as a starting point to create a nationally representative overview for objective 1.

**2. Describe and analyse how product specific RMMs** for the disease priority areas and active substances (see section 7) **have been integrated into relevant clinical guidelines** in DK, GR, LV, NL, PT and SI, identifying the key elements of risk minimisation included in new or updated clinical guidelines, key milestones and enablers and barriers for updating, time to integration, publication/dissemination, and adoption of guidelines in healthcare practice.

**3. Provide recommendations for regulators** to engage with healthcare professional bodies and other responsible parties to strengthen the role of clinical guidelines for RMM implementation, outlining feasible concrete steps EMA and national competent authorities could consider, where applicable to the country's context.

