## 9. Research methods

### 9.1. Study design

This qualitative study will employ a multiple-case study design using document analysis of clinical guidelines combined with qualitative interviews with key informants from the organizations/entities that produce guidelines in these specific countries as well as representatives from national competent authorities. Case study is a research design that has been widely used in social science research. In this study, we use a sub-type that is a multi-case design - in contrast to a single case design - which includes multiple cases selected according to a case selection strategy that aligns with the aims and objectives of the research. This study employs a diverse case selection strategy which is characterized by the selection of a set of cases intended to represent the full range of values along at least two dimensions (12). In this study the two dimensions are the five RMMs/TAs and the six countries outlined above. The purpose of selection strategy is to represent a maximum range of geographical diversity across EU members countries as well as maximum range of diversity of stakeholders across therapeutic areas that may be subject to RMMs. By contrasting and comparing the cases in the multi-case design, we learn about commonalities and variations. We also illuminate the potential reasons for these variations. The diverse-case selection strategy enables an in-depth of understanding of RMM implementation including its variation across the EU, which, in turn, allows for the identification of problems to deal with through research or regulatory intervention.

The combination of document analysis followed by semi-structured interviews utilizes the capacity of qualitative interviewing to explore subjective, non-observable dimensions of social relations or work processes to supplement and extend understanding of the results from preceding document analysis (13). The use of two sources of data also allows an ongoing validity assessment based on the convergence of information from the two sources.

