### **WP1. Mapping of organisations**

We will undertake a mapping exercise to identify and describe the relevant organisations/entities/national group(s) of experts issuing and updating clinical guidelines. Identification of organizations/entities/national group(s), hereafter called “entities”, will be identified by the national teams and will occur through five case studies. The five case studies (see section 7) represent a selection of medicinal products that are prescribed and dispensed by a broad range of health care professionals, from primary and secondary care as well as nurses and pharmacists. It is therefore to be expected that the case studies will provide a clear overview of RMM uptake in clinical guidelines for each country. An overview of entities that are involved issuing and updating clinical guidelines for each country will be produced. Clinical guidelines are defined as guidelines that summarise current medical knowledge and provide evidence-based treatment recommendations for specific therapeutic areas. This does not include drug monographs or drug information that is copied directly from the regulatory source (product information/label) without any clinical context or where no editing processes are applied (standards, website such as [Farmacotherapeutisch Kompas](#) (NL) and [pro.medicin.dk – information om medicin](#) (DK)).

In each country, the mapping proceeds by the following steps: 1) identification, 2) assessment of eligibility, and 3) description. The first step is identifying entities, extracting key information that allows for assessment of eligibility (WP1). In case of eligibility, these will proceed to WP2 and WP3 (see figure 3).

[figure not shown]

Figure 3. Process overview for mapping of entities that issue/update clinical guidelines and assessment of eligibility of clinical guidelines and key informants for inclusion in WP2 and WP3.

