In WP3 we will conduct a purposeful sampling of organizations and individuals within the countries and therapeutic areas whom we will engage for interview. The purposeful sampling strategy will be based on organisational mapping (WP1) and document analysis (WP2) with the aim to capture variation in processes, roles and responsibilities for updating clinical guidelines. Purposeful sampling is a strategy that is widely used in qualitative research to ensure the identification and selection of information-rich cases and the optimal use of limited resources (17). This includes identifying individuals or organizations that are particularly knowledgeable about the object of research. Purposive sampling differs from probabilistic or random sampling strategies that are typically employed to ensure the generalizability of findings through the minimization of potential selection biases. Although both qualitative and quantitative sampling methods are employed to maximize efficiency and validity, qualitative methods are typically employed to achieve depth of understanding whereas quantitative methods are employed to achieve breadth of understanding. (Patton, 2002). That is, qualitative methods emphasize saturation (i.e., reaching a comprehensive understanding by continuing to sample until no new substantive information emerges) whereas quantitative methods emphasize on generalizability (i.e., ensuring that the information gained is representative of the population from which the sample was drawn).

In WP3, we employ sequential sampling strategy that combines inclusive criterion-based sampling and complementary maximum variation-based sampling (18). The sequence is as follows: First, we identify which organizations to include based on the mapping exercise in WP1. Second, we identify which individuals to recruit for participation based on inclusion criteria. Third, we complement the criterion-based sample with relevant organizations to ensure that maximum variation of cases is captured.

The inclusion criteria for the stakeholder engagement are: 1) the entity that authored a guideline of

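### Section 8 promises a nationally representative overview for objective 1, but the design supports an overview for the five selected therapeutic areas only

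*Protocol*

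**What the plan says.** Section 8 of the protocol makes the five product-specific RMMs of objective 2 the starting point "to create a nationally representative overview for objective 1". Objective 1 has four items. Items c and d are tied to the five disease areas and active substances. Items a and b are not: item a asks for "Key bodies and organisations responsible for issuing clinical guidelines, including national guideline committees and any other responsible bodies at local, national or European level", and item b asks for triggers, processes and timelines for guidelines on pharmacological treatment in general.

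Section 7 gives two reasons for the choice of areas. The first is prominence: "Since these areas have been subject to prominent post-marketing risk communication". The second is that they span different diseases and hence different prescribers. Section 9.1 names the approach: "This study employs a diverse case selection strategy which is characterized by the selection of a set of cases" meant to cover the range along two dimensions, RMM or therapeutic area and country.

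Under WP1, entities are identified by way of the five case studies, and the protocol expects that "the case studies will provide a clear overview of RMM uptake in clinical guidelines for each country". Under WP3 it says: "Purposive sampling differs from probabilistic or random sampling strategies that are typically employed to ensure the generalizability of findings".

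**The concern.** To call an overview nationally representative is to say that what is found can stand for the country's guideline system as a whole. That needs either a frame covering the system or a sample drawn so that it reflects the system. The protocol describes neither. Its frame is set by five chosen RMMs, and its interviews are chosen for information and variation.

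What is at stake is how far the report may go. Objective 3 turns the findings of all three work packages into recommendations for EMA and the national authorities. If the phrase stays, statements about who issues guidelines and how they are updated in, say, Latvia or Portugal could be read as covering all pharmacological treatment there, when the evidence was gathered around five products.

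**Working it through.** There is no test, power or error rate here, so the check is mainly a comparison of sections, with a little counting.

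**The protocol's own figures.** Section 9.2.3 asks per country for at least 1 national competent authority, at least 1 public-sector body where possible, and at least 1 professional association for each of the 5 areas: 1 + 1 + 5 = 7. This matches the minimum of 7 in sections 9.4 and 9.5. Cases: 5 areas × 6 countries = 30, as in section 7. Interviews overall: 6 × 7 = 42 to 6 × 20 = 120. At the minimum there is one professional-association informant per country-by-area case: 30 informants for 30 cases.

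**Claim against frame.** Section 8, items 1a and 1b, concerns guideline bodies and updating processes without restriction by area. Section 9.1 (WP1) reaches entities through the five cases. Both substantive inclusion criteria in Table 2, for public-sector or expert bodies and for professional associations, refer to professionals involved in the five areas. Table 2 lists 13 medical specialties plus nurses and pharmacists. When WP1 restates item 1a from the tender specification, it adds a restriction to specific therapeutic areas that section 8 does not carry. The methods text is already narrower than the objective.

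**Claim against case selection.** Diverse-case selection (section 9.1) aims to span a range of values. It does not make the cases typical in their proportions. Prominent risk communication, one of the two stated reasons for the choice, is a further way in which the five may differ from other RMMs.

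**Claim against sampling.** The WP3 text defines generalisability as information being representative of the population sampled, assigns that emphasis to quantitative methods, and sets purposive sampling apart from it. On the protocol's own definition, the interviews do not supply representativeness.

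**Claim against stated limits.** Section 9.9 restricts generalisation only with respect to other Member States. The end of the WP3 text treats transfer to other disease areas as conceptual and leaves the judgement to the reader. Neither withdraws the within-country claim in section 8, and the second sits uneasily with it.

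**What cannot be computed.** The protocol gives no national count of guideline bodies, therapeutic areas or RMMs. No sampling fraction, coverage or bias can be derived.

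**The case against.** The best defence is that section 8 calls the five RMMs a starting point only, and that later steps widen the net. WP1 uses registers, web searches, guideline-based searches and snowballing, with the aim of including every stakeholder that issues guidance. Entities named in interviews are added. WP3 includes a complementary sample of organisations not specific to the therapeutic areas. The areas were chosen partly for breadth of disease and prescriber, and Table 2 is presented as an example of potential criteria. In a qualitative study, one adjective need not carry a statistical meaning.

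Much of this stands. The mapping is not a purposive sample: purposive sampling belongs to WP3, and WP1 aims to be exhaustive within its frame. The breadth is real. But exhaustive coverage within a five-area frame is not coverage of the national system, and the complementary interviewees bring in no RMMs from other areas.

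Two stronger readings are tempting and should not be made:

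- **That the mapping omits bodies listed in Appendix III whose specialties Table 2 does not name, such as urologists or dentists.** It does not. Table 2 admits associations reported by Member States, and section 9.2.2 says the Appendix III list enters WP1.
- **That uptake will be overstated because the five RMMs were prominent, so that the results are an upper bound.** No section says prominent RMMs reach guidelines more often. Uptake belongs to objective 2, which is expressly confined to the five areas, whereas the disputed phrase concerns objective 1.

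**Conclusion.** The point holds as a matter of scope. Section 8 states a property, national representativeness for objective 1, that the case selection, the eligibility criteria and the interview sampling do not provide and that the WP3 text in effect disclaims. The limitations section does not cover the gap within each country.

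Its size is the distance between five selected areas and all pharmacological treatment in each country, which the documents do not let one quantify. Neither the existence nor the direction of a bias is shown. National conclusions could be overstated if the wording is carried into the report; the documents do not establish that they would be. The conclusion assumes that the phrase is read in the sense the WP3 text itself gives to representativeness.

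**What to change.** 1. In section 8, replace the phrase with: *an overview of guideline-issuing entities and processes for the five selected therapeutic areas in each country*.
2. In section 9.1 (WP1), limit the expected overview of RMM uptake per country to the five selected RMMs.
3. In section 9.9, add that within each country the findings may not extend to other therapeutic areas or to less prominently communicated RMMs.
4. In the analysis and report, make country-level statements about processes only where informants describe the process as general to the entity or system.

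The cost is a few sentences and a less favourable claim. Mapping, document collection and interviews stay as planned.
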